6.5.4. Postdiscontinuation Anticancer Therapy

The number and percentage of patients with any additional postdiscontinuation anticancer treatment (PDT) including systemic, locoregional, and surgery will be presented for the ITT population by the treatment arm as well as by the region. Postdiscontinuation anticancer treatments will be summarized by therapy type and by drug name, and will also be reported in listings.

Imbalances between treatment arms in PDT use can confound the evaluation of the treatment effect for OS. If a notable imbalance in PDT use is observed (either overall or with respect to important agents or classes of agent), a sensitivity analysis for OS may be conducted in which patients will be reweighted in such a way as put more weight on patients with PDT in the arm that had less PDT use, and less weight on patients with PDT in the arm that had more PDT use, and thereby the rate of PDT use will be balanced between arms on a weighted basis. The PDT-weighted analysis will help assess the impact of any observed difference in the rate of PDT use between arms.

Additional analysis may be explored to help interpret OS results, for example, analysis of OS censoring at the start of PDT.

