7.3. Discontinuation

The reason for discontinuation and the date of discontinuation will be collected for all patients. All randomized patients who discontinue, regardless of whether or not they received study treatment, will have procedures performed as shown in the Study Schedule ([Attachment 1](#)).

Patients who are discontinued from study treatment early will have follow-up procedures performed as shown in the Study Schedule ([Attachment 1](#)).

If a patient withdraws informed consent, he or she must not be contacted unless he or she has explicitly provided permission and consent. Lilly may continue to use previously collected medical research data prior to the withdrawal consistent with the original authorization.

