7.3.2. Discontinuation of Study Treatment

Patients will be discontinued from study treatment in the following circumstances:

- The patient is enrolled in any other clinical trial involving an investigational product or in any other type of medical research judged not to be scientifically or medically compatible with this study.
- The patient, for any reason, requires treatment with another therapeutic agent that has demonstrated effectiveness for treatment of the study indication, discontinuation from study treatment will occur prior to introduction of the new agent.
- The patient requests to be withdrawn from study treatment.
- The patient is significantly noncompliant with study procedures and/or treatment.
- The investigator decides that the patient should be discontinued from study treatment.
- Unacceptable toxicity. Refer to [Table JVDE.3](#) and to [Table JVDE.4](#) for information about discontinuation from study treatment due to AEs.
- Any study treatment-related event that is deemed life-threatening, regardless of NCI-CTCAE grade, if the event is considered possibly related to study treatment.
- The patient requires any of the following:
 1. >2 dose reductions
 2. ≥ 2 consecutive missed doses of study treatment
 3. a dose delay of >21 days

In the case of 2 or 3 above, continuation of study treatment may be considered, however, subject to the requirements stated in Section 9.4.2.

- A deterioration in ECOG PS to 3 or worse during the course of therapy on study despite optimal supportive care, even in the absence of radiographic evidence of disease progression.
- Disease progression (assessed radiologically or clinically). If the patient is experiencing a treatment benefit in the opinion of the investigator, the patient may continue study treatment beyond radiographic progression until clinical progression. Determination of clinical progression is at the discretion of the investigator and may include both objective and subjective data.

If treatment is discontinued for any reason other than radiographically confirmed progressive disease (PD) or withdrawal of consent, radiographic tumor assessments will continue according to the protocol schedule, except when not feasible, in the opinion of the investigator, because of the patient's clinical status.

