9.6. Concomitant Therapy

Appropriate documentation of all forms of premedications, supportive care, and concomitant medications must be captured on the CRF at each visit. Concomitant medications and supportive care therapies must also be documented at the time of discontinuation and at the 30-day short-term follow-up visit.

A list of restricted and excluded medications is provided in [Attachment 9](#). No chemotherapy, experimental medications, other systemic anticancer therapy, immunotherapy, hormonal cancer therapy, or curative surgery or procedures for cancer will be permitted while patients are on study treatment.

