6.4.2. Efficacy Definitions and Data Handling

6.4.2.1. Overall Survival

The OS time is defined as the time from the date of randomization to the date of death from any cause. If a patient is not known to have died on or before the date of data cut-off, OS data will be censored on the last date (on or before the cut-off date) the patient was known to be alive.

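### SAP 6.5.4: the optional PDT-weighted OS analysis, read plainly, weights the whole survival time by a later status that requires survival, so its HR can be biased even if PDT does nothing (low priority)

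*SAP*

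**What the plan says.** SAP 6.5.4 tabulates the number and percentage of patients with any PDT (systemic, locoregional or surgical) by arm. It then adds a conditional analysis: "If a notable imbalance in PDT use is observed", an OS sensitivity analysis may be run with reweighted patients. The rule is to "put more weight on patients with PDT in the arm that had less PDT use", and to give less weight to PDT patients in the arm with more use, so that "thereby the rate of PDT use will be balanced between arms on a weighted basis". The result is offered as a help in judging the impact of the imbalance. As a further possibility the section names an "analysis of OS censoring at the start of PDT". It gives no weight formula, time-varying weight, landmark, predictor of PDT or variance method.

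Three other places fix the time order:
- SAP 6.4.2.1: "The OS time is defined as the time from the date of randomization to the date of death from any cause".
- Protocol 7.3.2, when a patient needs another agent effective in this indication: "discontinuation from study treatment will occur prior to introduction of the new agent".
- Protocol 9.6: no chemotherapy, other systemic anticancer therapy "or curative surgery or procedures for cancer will be permitted while patients are on study treatment".

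**The concern.** The balancing target is a rate of PDT use, and the section has just defined that rate as the share of patients with any PDT. The natural reading is therefore one weight per patient, set by arm and ever/never PDT, applied from randomization onward.

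A patient can be in the PDT group only by living through study treatment and any gap before the next therapy. Patients who die early are in the no-PDT group by construction. Raising the weight of PDT patients in the low-use arm thus adds long survivors to that arm, and lowering it in the high-use arm removes them there. This is immortal-time bias, and it does not need PDT to have any effect.

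What is at stake is interpretation. The analysis is triggered by an imbalance, and the imbalance is what creates the bias. A reader could credit PDT with an effect that the weights produced.

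**Working it through.** **1. Plan's own figure.** Inputs from SAP 6.2.2: HR 0.67, 2:1 allocation, two-sided alpha 0.05, power 80%. Deaths = (1.960 + 0.842)² / [(2/3)(1/3)(ln 0.67)²] = 7.85 / (0.2222 × 0.1604) ≈ 220.2, so 221 as stated. The SD of the ITT log HR is about 1/√(221 × 2/9) = 1/√49.1 = 0.14.

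**2. Mechanism by hand.** Assume no drug effect and inert PDT, median OS 4.5 months in both arms, median time to discontinuation 2 months, median gap to PDT 1 month, discontinuation independent of death, and uniform censoring at 6-30 months. Willingness to take PDT is 30% on ramucirumab and 50% on placebo. Simulated PDT rates are then 16.8% and 28.1%. The ramucirumab means below come from the mirror-image run, in which placebo has the 30% willingness; with no drug effect the process is the same.

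Pooled rate = (2 × 16.8 + 28.1)/3 = 20.6%. Weight = pooled rate / arm rate, by PDT status.

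| Group | Mean observed OS, months | Weight |
|---|---|---|
| Ramucirumab, PDT | 8.43 | 20.57/16.8 = 1.22 |
| Ramucirumab, no PDT | 5.26 | 79.43/83.2 = 0.95 |
| Placebo, PDT | 8.51 | 20.57/28.1 = 0.73 |
| Placebo, no PDT | 4.77 | 79.43/71.9 = 1.10 |

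Unweighted means: ramucirumab 0.168 × 8.43 + 0.832 × 5.26 = 5.79; placebo 0.281 × 8.51 + 0.719 × 4.77 = 5.82, equal apart from simulation noise. Weighted means: 0.2057 × 8.43 + 0.7943 × 5.26 = 5.91 against 0.2057 × 8.51 + 0.7943 × 4.77 = 5.54. The weights alone open a gap in favour of the arm with less PDT. The weighted Cox HR in this run was 0.92; the unweighted HR was 1.00.

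**3. Size over a range.** The documents give no PDT rates or timing, so these are assumptions: exponential OS with a placebo median of 4.5 months, inert PDT, 2-month median to discontinuation, 0.75-month gap, and correlation between discontinuation and death from 0 to 0.7. Ranges also cover more than one censoring pattern (for example 20-month accrual with cutoff at 221 deaths, or uniform 4-24 months).

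| PDT, ramucirumab/placebo | True HR 1.00 | True HR 0.67 |
|---|---|---|
| 18%/30% | 0.92-0.95 | 0.62-0.64 |
| 18%/37% | 0.87-0.92 | 0.59-0.62 |
| 30%/18% | 1.05-1.08 | 0.70-0.72 |
| 5%/15% | 0.94-0.96 | not run |
| 24%/24% | 1.00 | not run |

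In SD units: |ln 0.96|/0.14 = 0.29; ln(0.70/0.67)/0.14 = 0.31; |ln 0.92|/0.14 = 0.60; |ln 0.87|/0.14 = 0.99. The table spans roughly 0.3 to 1.0 SD. Varying the discontinuation median (1-3 months), gap (0-1.5 months) and correlation (0 or 0.7) widens the null ranges for the first three rows to 0.88-0.99, 0.81-0.98 and 1.01-1.12.

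**4. Control.** With PDT status fixed at time 0, so that survival is not required, the weighted HR is 1.00 at all rates. The survival requirement causes the bias, not the weighting itself.

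**5. Where it disappears.** With discontinuation at a random 30-80% of survival and a true HR of 1.00, the weighted HRs at 18%/30%, 18%/37% and 30%/18% are about 1.02, 1.03 and 0.98 with no gap, 1.00 for all with a 0.25-month gap, and 0.97, 0.94 and 1.03 with a 0.75-month gap.

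**6. If PDT works.** If PDT cuts later hazard by 30% and the drug has no effect, ITT gives 1.03-1.04, 1.05-1.06 and 0.97 at the same three rates. The weighted HR gives 0.92-0.95, 0.87-0.91 and 1.05-1.07, further from 1.00 on the other side. At a 50% cut the two are about equally far off.

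**7. Alternatives, true HR 1.00, inert PDT, same rates.** Plain censoring at PDT start gives 1.00 at correlation 0; 1.06, 1.11 and 0.94 at 0.7; and 1.13-1.15, 1.23-1.24 and 0.89-0.90 with discontinuation at 30-80% of survival. Adding by-arm weights (the inverse of the Kaplan-Meier estimate of PDT start since discontinuation) gives 1.00 in all of these.

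**The case against.** The strongest reply is that little hangs on this. The analysis needs a notable imbalance and even then is only permitted. It is not among the five planned OS sensitivity analyses in SAP 6.5.3.2, and no test is attached. The blind is kept at progression (Protocol 9.5), so a large imbalance may never arise. With equal prescribing and a true HR of 0.67, longer survival alone gives PDT rates such as 28%/24% or 33%/28%, and the weighted HR is 0.68 to 0.70. All of this stands and sets the priority low.

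Second, SAP 6.5.4 never says that the weights are fixed or ever/never, so time-updated weights are not excluded. That is true. A reader might infer that the SAP commits to the biased version; it does not. But equal rates of use are its only stated target, and the section does not mention the survival condition.

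Third, sizes rest on assumed timing, and the direction can vanish or slightly reverse. This also stands. A reader might infer that the analysis always favours ramucirumab, or always the low-use arm; neither follows.

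Fourth, the replacement is imperfect. The discontinuation-time weights are right only under their own assumption. If the odds of PDT are three times higher in patients who will live over 3 months after discontinuation, and this is unrecorded, they give 0.96, 0.93-0.94 and 1.04-1.05, against 0.89-0.91, 0.83-0.86 and 1.09-1.11 for the fixed weights. With the opposite and less plausible selection (18%/30%, independent discontinuation, 0.25-month gap) they do worse: 1.05 against 0.98. They also change the question from balanced PDT to no PDT.

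**Conclusion.** The concern holds as a low-priority point about interpretation. On the plain reading of SAP 6.5.4, the PDT-weighted HR can move by roughly 0.3 to 1.0 SD of the ITT log HR in the tabulated unequal-rate scenarios while PDT does nothing. With a clear gap before PDT, the shift usually favours the arm with less PDT. These figures rest on assumed PDT rates, discontinuation times and gaps, and are not predictions for this trial.

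A reader might go further and infer that the OS conclusion or the error control is compromised. The documents do not support that. The primary test is the stratified log-rank test in the ITT population without these weights (SAP 6.5.3.2), and the gatekeeping sequence (SAP 6.5.3.3) does not use them.

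**What to change.** In SAP 6.5.4, rule out weights based on ever/never PDT over the whole OS time. Then choose one of two options before unblinding:
- Drop the PDT-weighted HR and read ITT OS beside the PDT table.
- If a PDT-adjusted OS is shown, treat PDT as time-dependent, for example by censoring at PDT start with by-arm weights from time since discontinuation. Label it supportive. State that it estimates OS without PDT and assumes PDT start is unrelated to prognosis given what is adjusted for. Do not rely on plain censoring alone.

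The main data are planned: "The reason for discontinuation and the date of discontinuation will be collected for all patients" (Protocol 7.3), and PFS censoring (SAP Table 3) already needs the start of new anticancer treatment. The cost is a few sentences and some programming, the loss or replacement of one optional analysis, and some precision (SD of log HR 0.15-0.19 against 0.14-0.15). Two limits remain. Long-term follow-up asks only for systemic PDT (Protocol 10.1.2; Attachment 1, footnote t). ECOG PS and AFP are not scheduled there, so bias remains if unrecorded prognosis drives late PDT.

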6.5.5. Patient-Focused Outcomes

For each of the instruments, compliance will be summarized for the ITT population. Compliance at an assessment time point is defined as the number of patients who provided data divided by the expected number of patients on study at that time point. A patient who answers at least one item at a time point is considered to have been assessed. Compliance will be summarized by time point, and reasons for non-compliance will be tabulated. Compliance at different time points along with the reasons for noncompliance may be represented graphically using a stacked bar chart.

6.5.5.1. FHSI-8 Analyses

The proportion of patients in each arm with deterioration in scores, improvement in scores, and stable scores at specific time points will be presented both in a summary table and graphically using stacked bar charts. The proportion of patients who deteriorated at each assessment time point may be compared using Fisher's exact test. Patients with no data will be considered deteriorated.

FHSI-8 score will be summarized descriptively at each assessment time by treatment arm, as well as changes from pre-treatment visit, provided at least 30% of the patients have an FHSI-8 score at that time point. Best and worst responses across all the visits will also be summarized in a table.

The time to deterioration of FHSI-8 individual item will be compared between the treatment groups from stratified and unstratified log-rank tests. The HR and 95% CIs will be estimated using Cox's PH model, covariates may include assigned treatment and baseline score.

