10.2. Health Outcome/Quality of Life Measures

The assessment of patient-reported outcomes, including disease-specific symptoms and health status, will be assessed using the Functional Assessment of Cancer Therapy (FACT) Hepatobiliary Symptom Index-8 (FHSI-8) and the EuroQol 5-Dimension 5-Level (EQ-5D-5L). The instruments will be administered together with the FHSI-8 presented first, followed by presentation of the EQ-5D-5L. Patients will complete the instruments only if the instruments have been translated into a language in which the patient is fluent and the translation has been validated. Refer to the Study Schedule ([Attachment 1](#)) for the specific timing of these assessments.

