- w The FHSI-8 and EQ-5D-5L are the PRO measures for this study. The instruments should be completed at the beginning of each specified visit, before any extensive contact and consultation with study site personnel because such encounters may bias patient responses. The instruments will be administered together, with the FHSI-8 presented first followed by presentation of the EQ-5D-5L. Administer at baseline. Administer during the treatment period, every 6 weeks (± 3 days) after randomization and administer at the beginning of short-term follow-up.
- x Treatment should begin within 7 days after randomization. In Cycle 1, administer on Day 1. Thereafter, administer on Day 1 (± 3 days) of every cycle.
- y The scheduled assessments on Days 1-7 of the short-term follow-up period may also be performed on the same day the patient and the investigator agree that the patient will no longer continue study treatment.
- z Cycle 3, 6, 9, 12, etcetera.

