6.3. Analysis Populations

6.3.1. *Intent-to-Treat (ITT) Population*

The ITT population will comprise all randomized patients. This population will be assessed for baseline characteristics and efficacy including quality of life (QoL). The ITT analysis of these data will consider allocation of patients to treatment groups as randomized regardless what actual treatment they receive.

6.3.2. *Safety Population*

The Safety population will include all patients who received at least 1 dose (including a partial dose) of an investigational product (ramucirumab or placebo). Analysis of safety data will be based on the Safety population and will be performed based on the actual treatment a patient received on the first study treatment administration regardless of which treatment they were randomized to receive (“as treated”).

6.3.3. *Per-Protocol (PP) Population*

Per-protocol population will include all patients who are randomized and treated and do not have any major protocol violations that could potentially affect the efficacy conclusions of the study. Efficacy analyses will also be performed in the PP population. The PP population is a subset of the ITT population that will be defined and finalized prior to database lock for the final analysis. Patients who meet any of the following criteria will be excluded from the PP population:

- Randomized but never received study medication
- All AFP < 400 ng/mL prior to first dose, as determined by local and/or central laboratory testing [per Inclusion Criterion (IC) 9]
- Baseline Child-Pugh (CP) score was not 5 or 6 (CP class A) [per IC 7]
- Patient does not have HCC that is Barcelona Clinic Liver Cancer (BCLC) Stage B or C at randomization [per IC 8]
- Did not have a diagnosis of HCC as defined in the protocol [per IC 1 and EC 17]
- Had not been treated with sorafenib
- Had an ECOG PS score of 2 or above at enrollment [per IC 10]
- Received any previous systemic therapy with vascular endothelial growth factor (VEGF) inhibitors or VEGF receptor inhibitors (including investigational agents) other than sorafenib for treatment of HCC [per Exclusion Criterion 23]
- Received additional concurrent chemotherapy, biological response modifiers, other investigational agents, and radiation therapy (except for palliation to symptomatic sites of disease) during the study treatment
- The patient has a history of or current hepatic encephalopathy (any grade) or current ascites (Grade ≥ 2)

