6.4.2.3. Time to Deterioration in FHSI-8

Time to deterioration in FHSI-8 total score is defined as the time from the date of randomization to the first date observing a decrease of ≥ 3 points from baseline. In case of no FHSI-8 deterioration, the subject will be censored at the time of the last FHSI recording. Additionally, the deterioration threshold and clinically meaningful difference will be evaluated in the trial population as described in the Psychometric Statistical Analysis Plan.

The deterioration criteria that FHSI-8 total score decrease of ≥ 2 or 4 points will be used as sensitivity analyses.

Other patient-focused outcome analysis is defined in Section 6.4.2.7.

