Additionally, patients' health status will be assessed using EQ-5D-5L. EuroQol – 5 Dimensions index score is calculated from a set of item weights to derive a scale of 0 to 1, with 0 representing death and 1 representing perfect health, with the possibility of negative scores. The index score will be based on the value set for England, where the lowest possible value is -0.281 (Devlin et al. 2017). The visual analog scale (VAS) is scored from 0 (*worst imaginable health state*) through 100 (*best imaginable health state*) to represent the patient health condition.

For FSHI-8 and EQ-5D-5L, other than baseline visit and end of treatment visit, a visit window is applied. If the actual assessment date falls in the window of study days $[(X-1)*7-20, (X-1)*7 + 21]$, where $X = 7, 13, 19, \dots$, the visit will be presented as Week X. If there are multiple assessments within 1 visit window, the last assessment will be used in the summary by visit.

For percentage compliance of the FSHI-8 and EQ-5D-5L, instruments with at least 1 item completed will be considered as having been completed. No other adjustment or imputation for missing data will be performed. To evaluate the impact of missing data on results, sensitivity analyses will be performed from the following imputations: last observation carried forward, worst observation carried forward, and multiple imputation using Markov Chain Monte Carlo methodology.

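### Counting patients with no FHSI-8 data as deteriorated makes the by-visit symptom comparison, from about week 13, mainly a comparison of death and treatment discontinuation

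*SAP*

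**What the plan says.** SAP 6.5.5.1 will present, in a table and in stacked bars, "The proportion of patients in each arm with deterioration in scores, improvement in scores, and stable scores at specific time points". It then says "The proportion of patients who deteriorated at each assessment time point may be compared using Fisher's exact test", followed directly by "Patients with no data will be considered deteriorated". The display is planned unconditionally; only the test is optional. SAP 6.3.1 assigns quality-of-life data to the ITT population, so the natural denominator is all randomized patients.

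Other parts of the plan determine who can have data:

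- **Collection.** Protocol Attachment 1, footnote w, schedules the questionnaires at baseline, every 6 weeks on treatment, and then "administer at the beginning of short-term follow-up". Long-term follow-up (Protocol 10.1.2) gathers survival and later anticancer therapy, not questionnaires.
- **Visit windows.** SAP 6.4.2.7 assigns forms to Weeks 7, 13, 19 and so on, but keeps the end-of-treatment form outside these windows.
- **Translation.** Protocol 10.2: "Patients will complete the instruments only if the instruments have been translated into a language in which the patient is fluent", and the translation must also be validated.
- **Definition.** SAP 6.4.2.7 defines deterioration as a fall of at least 3 points from baseline.
- **Missing data.** SAP 6.4.2.7 also states "No other adjustment or imputation for missing data will be performed", then lists three imputation methods as sensitivity analyses. SAP 6.4.3 allows imputation where it is specified.
- **Confirmatory endpoint.** In time to deterioration in FHSI-8 (SAP 6.4.2.3), if no deterioration occurs, "the subject will be censored at the time of the last FHSI recording".

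**The concern.** Three kinds of patient have no score at a given visit: those who have died, those alive but off treatment, and those still on treatment who missed a form. The rule gives all three the same label as a patient whose score fell by 3 points. For the second group the label has no observed basis, because the schedule stopped asking. Patients on treatment at data cut-off whose visit is not yet due are not exempted either.

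If the arms differ in survival or time on treatment, the by-visit proportions differ even when symptoms among assessed patients are identical. The table would stand beside a confirmatory FHSI-8 endpoint and could be taken as supporting evidence on symptoms.

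**Working it through.** **Design inputs.** SAP 6.2.2 gives HR 0.67, median OS 6.7 months (ramucirumab) and 4.5 months (placebo), 186 and 93 patients, two-sided alpha 0.05 and 80% power. The by-visit comparison has no stated figure of its own, so I first checked that these inputs reproduce the event count:

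(1.960 + 0.842)² / [(2/3)(1/3)(ln 0.67)²] = 7.849 / 0.03564 = 220.2, rounded up to 221 deaths, as stated.

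**Formula.** Let d be the true deterioration rate among patients with a score, set equal in both arms. Under the SAP rule:

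P(counted as deteriorated) = 1 − S(t)(1 − d), with S(t) = 2^(−t/median) and t = (week − 1) × 7 / 30.4375 months.

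Exponential survival and d = 30% are my assumptions.

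**Step 1: death as the only cause of no data.** At week 19, t = 126 / 30.4375 = 4.14 months.

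- Ramucirumab: S = 2^(−4.14/6.7) = 0.652; 1 − 0.652 × 0.70 = 54%.
- Placebo: S = 2^(−4.14/4.5) = 0.529; 1 − 0.529 × 0.70 = 63%.

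Each cell gives ramucirumab vs placebo:

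| Visit | No data (dead) | Counted as deteriorated | Share of the deteriorated with no data |
|---|---|---|---|
| Week 7 | 13% vs 19% | 39% vs 43% | 34% vs 44% |
| Week 13 | 25% vs 35% | 47% vs 54% | 52% vs 64% |
| Week 19 | 35% vs 47% | 54% vs 63% | 64% vs 75% |
| Week 25 | 44% vs 57% | 60% vs 70% | 72% vs 82% |

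The last column is the second divided by the third. At week 19, exact enumeration of the Fisher test gives p < 0.05 in 26% of trials. With d = 20% the week 19 figures are 48% vs 58%; with d = 40% they are 61% vs 68%. At d = 40% the week 13 share with no data falls to 45% vs 57% (0.248/0.549 and 0.346/0.608), so the majority claim is borderline there on death alone.

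**Step 2: add treatment discontinuation.** The documents give no time on treatment, so these medians are assumptions. Now S(t) is the proportion still on treatment, d = 30%, and at week 13 t = 84 / 30.4375 = 2.76 months.

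| Assumed median time on treatment | Counted as deteriorated | Share with no data | Fisher p < 0.05 |
|---|---|---|---|
| 3.0 vs 2.0 months | 63% vs 73% | 75% vs 84% | about 36% |
| 4.0 vs 2.0 months | 57% vs 73% | 67% vs 84% | about 76% |
| 2.0 vs 2.0 months | 73% vs 73% | 84% vs 84% | no artefact |

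**Step 3: can the sign reverse?** Suppose true deterioration among assessed patients is worse on ramucirumab, 40% vs 30%. At week 13 with 4.0 vs 2.0 months, the rule gives 1 − 0.620 × 0.60 = 63% against 1 − 0.384 × 0.70 = 73%. The arm with more symptom deterioration looks better.

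**Step 4: contrast with observed scores.** In the 4.0 vs 2.0 month case about 115 (186 × 0.620) and 36 (93 × 0.384) patients have a week 13 score. With d = 30% in both arms, the Fisher test on these patients rejects in 3.8% of trials, against 76% under the rule. This sizes the artefact; it is not a replacement analysis, because those patients are selected by surviving and staying on treatment.

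**The case against.** **Stakes.** The test is optional and outside the sequence OS, PFS, FHSI-8, ECOG PS. The FHSI-8 endpoint in that sequence does not use this rule. A reader might infer that the confirmatory FHSI-8 result or the study-wise error rate is compromised; the documents do not support that. This point stands and limits the weight of the concern.

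**Missing-data rules.** A reader might see a flat contradiction with the no-imputation sentence. SAP 6.4.3 allows specified exceptions, and the sentence in 6.4.2.7 directly follows the definition of questionnaire compliance. At most a cross-reference is missing.

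**Different handling in the time-to-event analysis.** A by-visit summary and a time-to-event analysis may treat missing data differently. Nor are all patients off treatment censored there: one who has already fallen by 3 points is an event. This stands. The SAP also counts patients without a tumor assessment as non-responders for ORR and DCR. That parallel is weaker: imaging continues after treatment stops until radiographic progression (Protocol 10.1.2), whereas FHSI-8 does not.

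**Ambiguity.** No data could mean none at all rather than none at that visit. Most patients who stop treatment would then escape the label through the end-of-treatment form. But the sentence directly follows a comparison made at each time point, so the by-visit reading is the natural one. The ambiguity itself needs correcting.

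**Existing safeguards.** SAP 6.5.5 tabulates compliance and reasons for non-compliance, over patients expected on study. SAP 6.5.5.1 summarizes observed scores where at least 30% of patients have one. Both help a careful reader, but neither changes the proportions or the test, and the 30% floor is not written for them.

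**Translation.** Lack of a validated translation is fixed before randomization and should balance between arms. It dilutes the comparison but does not favour an arm.

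**Conclusion.** The concern holds for the by-visit FHSI-8 proportions and the optional test on them. From about week 13 the figure labelled deteriorated would consist mostly of patients without a score, and it moves with survival and time on treatment rather than with symptoms alone. At week 7 the effect is smaller.

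The firmest size is the death-only result at week 19: 54% vs 63%, a 9-point gap with no symptom difference among assessed patients. It uses the SAP's own OS medians but still assumes exponential survival and 30% deterioration. The larger figures depend on assumed treatment durations and are illustrative.

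Two stronger readings are tempting. One is that the rule favours ramucirumab. The documents do not say which arm stays on treatment longer: the design hypothesis gives ramucirumab longer survival, equal time on treatment removes the artefact in Step 2, and earlier stopping on ramucirumab would reverse it. The other is that 26% is a false-positive rate. Survival truly differs in that scenario, so a test that counts death is detecting something real. The error lies in reading it as a symptom difference.

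This is a correction to a supportive analysis. It is worth making because the display is planned unconditionally and its label would mislead.

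**What to change.** Replace the sentence in SAP 6.5.5.1 with these rules:

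1. Over all randomized patients at each visit, show improved, stable and deteriorated from an observed score. Show as separate categories: died; off treatment and not assessed; not yet due at data cut-off; no validated translation; missed while due.
2. Give the number with a valid score per arm and visit. State that proportions among those patients are subject to survivor selection.
3. Do not apply the Fisher test to a pooled category that counts no data as deteriorated and present it as a symptom comparison. If a composite is tested, define it explicitly (for example, deterioration or death) and label it so.
4. Define no data as none at that visit, and cross-refer to SAP 6.4.2.7 and 6.4.3.

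The cost is SAP wording and table layout. Dates of death, treatment discontinuation and cut-off are already needed elsewhere, and reasons for non-compliance are already to be tabulated. The one point to check is whether the recorded reasons identify patients without a validated translation; the documents do not say.
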